The Video Interaction Guidance (VIG) programme is being implemented between March 2021 (with intake from July 2021) and June 2022 in four English Local Authorities (LAs). VIG is a relationship based parenting intervention in which a VIG practitioner films a parent and child interacting in short, one-to-one sessions. By providing feedback on these sessions based on edited clips of better than usual moments, VIG aims to promote parental sensitivity, child attachment and longer term social and emotional development.

The intervention developer, Babies 1st, will train and supervise 21 VIG Practitioners across the four LAs. Practitioners will undertake the role in addition to their substantive role (e.g. social or family worker) and will each work with a minimum of six families (typically a focal parent and infant dyad) over eight sessions or more.

The programme is being evaluated by IFF Research and the Policy Evaluation and Research Unit (PERU) at Manchester Metropolitan University (Man Met). The evaluation comprises impact, implementation (process) and cost components. The impact study design is a pragmatic, multi-site, effectiveness trial, with individual family dyads allocated to intervention and control within sites, at random, on a 1:1 intervention to control basis. Families allocated to the intervention group will receive VIG in addition to their usual care; those in the control group will receive usual care only. All families will be asked to complete a baseline questionnaire containing psychometric measures prior to randomisation and also at four months post-randomisation. In addition, LAs will supply child protection outcomes from administrative data six months post-randomisation.

Intake will begin in August 2021 and will continue until the end of March 2022. Randomisation will begin in July 2021, and the intervention for all families will end by June 2022. An evaluation report will be published by the end of August 2022.

The evaluation includes a review point (September 2021) to allow for changes to the protocol and evaluation activity on account of factors which are currently unknown (e.g., the amount of dropout and proportion of parents requiring translation services or additional support to complete the survey). For further details see p.12.

Table of Contents

Background and Problem Statement	6
Intervention and Theory of Change	6
Logic Model	9
Interventions	10
Mechanisms	10
Outcomes	10
Impact Evaluation	11
Research Questions	11
Design	12

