meeting, followed by three cycles of VIG and a final evaluation and feedback session. Each cycle consists of one session where the social worker films interactions between the parent and child and a Shared Review where the social worker highlights examples of positive interactions and encourages the parent to reflect on what they did well, what they can learn and how to replicate positive behaviour. Each session lasts around 45 minutes.

Logic Model⁴

⁴ Version 2

Interventions

The intervention will be delivered by 21 social and family workers in four local authorities. The social and family workers will be trained in VIG by Babies1st and the training will consist of an introductory training and follow-up workshop as well as fortnightly individual and monthly group supervision sessions, plus a Midpoint Review Day and Accreditation Day with external AVIGuk accredited trainers.

As part of their training, social and family workers have been supported to complete the VIG intervention with at least one 'pilot' family, under close supervision of a qualified VIG practitioner from Babies1st.

The intervention includes a minimum of eight sessions between the social and family worker and parent dyad, over the course of 3-4 months. The eight sessions consist of an initial introductory meeting, followed by three cycles of VIG and a final evaluation and feedback session. Each cycle consists of one session where the social and family worker films interactions between the parent and child and a Shared Review where the social and family worker highlights examples of successful interactions and encourages the parent to reflect on what they did well, what they can learn and how to replicate positive behaviour. Each session lasts around 45 minutes.

Mechanisms

During the Shared Reviews, the parent will be encouraged to reflect on themselves as a parent and the responsibilities that comes with this. They are also supported to be more aware of and reflect on their baby's needs. They will be encouraged to identify ways in which they are already responding sensitively to these needs, as well as opportunities to apply this positive behaviour to more stressful parenting situations.

The family and social worker supports the parent to celebrate and understand examples of sensitive parenting, encouraging the parent to feel proud of these moments.

Outcomes

It is hypothesised that the intervention will lead to the following short term outcomes:

- Higher parental self-esteem

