We will undertake exploratory analysis to explore VIG Practitioner outcomes. As defined by the Logic Model these pertain to engagement and job satisfaction. This analysis is exploratory due to the absence of a counterfactual group (the evaluation commissioning process did not allow for random allocation of social and family workers to VIG Practitioner training), and the small sample size (n = 21).

These outcomes will be explored using the psychological construct of work engagement. This is understood by occupational psychologists to be the opposite of burnout; engaged employees are connected with and energised by their work, and they are able to deal effectively with the demands of their job. The Shortened Utrecht Work Engagement Scale (UWES-9)¹⁹ is a self-report questionnaire comprising 9 items measuring three dimensions which constitute work engagement. Examples of scale items are:

“When I get up in the morning, I feel like going to work.” (*vigor*)

“I am proud of the work that I do.” (*dedication*)

“Time flies when I am working.” (*absorption*)

Vigor, associated with high levels of energy and mental resilience while working, the willingness to invest effort in one’s work, and persistence even in the face of difficulties. *Dedication* refers to being strongly involved in one’s work and experiencing a sense of significance, enthusiasm, inspiration, pride, and challenge. *Absorption*, characterised by being fully concentrated and happily engrossed in one’s work, whereby time passes quickly and one has difficulties with detaching oneself from work.

Items are rated on a 6–point Likert scale (1 = almost never , 6 = always). Dimension scores are obtained by calculating the mean of the items in the subscale. The overall work engagement scale score is obtained by calculating the mean of all 9 items.

The instrument will be administered to VIG Practitioners either as part of face-to-face interviews or by email before delivery commences (in early July 2021) and again in February 2022.

VIG Practitioner overall mean and dimension mean scores will be compared pre- and post-intervention and will also be compared with a reference norm group.

Contextual Factors Analysis

Contextual factors will be explored within the context of the implementation and process evaluation and will not be quantified for analysis of impacts.

Evaluation Review Point

¹⁹ Schaufeli, W. B., & Bakker, A. B. (2004). ‘Bevlogenheid: Een begrip gemeten.’ *Gedrag en organisatie*, 17, 89-112.

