2. Is the training perceived by VIG practitioners as adequately equipping them to deliver VIG?	

 - How prepared/ confident do VIG Practitioners feel to deliver VIG? - What support needs do VIG Practitioners have throughout the intervention? 	In-depth interviews with delivery leads, trainers and VIG Practitioners at the end of setup/implementation and at the end of delivery
3. How have social workers experienced delivery of VIG?	

 - How do VIG Practitioners describe the experience of delivering VIG? - What went well and what went less well? - Can VIG Practitioners identify any areas of improvement? 	In-depth interviews VIG Practitioners at the end of setup/ implementation and at the end of delivery
4. What difference is VIG perceived to make to parents and why?	

 - How have parents experienced VIG? - What elements of VIG did parents find most/least useful? - What difference is VIG perceived to make to parents, and why? (e.g. parents' relationship to the focal child and to other children in the family; experience of parenting; relationship to social services) - When/for who is VIG perceived to be most effective? 	In-depth interviews with parents at the end of delivery
5. What difference is VIG perceived to make to VIG Practitioners and why?	

 - What difference is VIG perceived to make for VIG practitioners, and why? (e.g. ability to support families; engage with families; engagement with their work; job satisfaction) - What social worker characteristics/factors are perceived to influence VIG delivery? 	In-depth interviews VIG Practitioners the end of delivery
6. When / for who is VIG perceived to be most effective?	

 - What parent characteristics/factors are perceived to be related to effective VIG? - What social worker characteristics/factors are perceived to influence VIG effectiveness? 	In-depth interviews with delivery leads, trainers, VIG Practitioners at the end of setup/implementation and delivery leads, trainers, VIG

Methods

Sample and Recruitment

Sample

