- **Focus groups with VIG Practitioners** in each area. In areas with more than 6 VIG Practitioners taking part, focus groups will be split into two groups, totalling six groups. The discussion will focus on their expectations of the programme, views on the training and guidance they have received and what ongoing support they feel they need.

Qualitative data collection will take place in August 2021, shortly after intake.

Qualitative data collection - stage 2

The second phase of fieldwork will include:

- **Visits to each of the participating areas** to carry out interviews with delivery leads and all 21 participating VIG Practitioners. For this phase, we will conduct interviews with VIG Practitioners on a one-to-one basis, to give sufficient time to be able to discuss detailed experiences with specific parent dyads without fear of disclosure to others. Any VIG Practitioners unable to participate on the day of the visit will be interviewed by video call at their convenience. In addition to exploring issues around process, VIG Practitioners will be asked a few more quantitative questions about impact e.g., self-reported 'work engagement' etc. As this group is small and not being randomised this is a proportionate approach to obtaining impact measures. We will however make exploratory comparisons between VIG practitioners' outcomes and those of established norm groups reported by test developers.
- **A focus group with supervisors over video call and observations of four group supervision sessions**, to better understand any challenges or support needs among VIG Practitioners and how these are met.

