- **In-depth interviews with 24 families.** In order to capture the experiences of parents and their views on the outcomes achieved, we will carry out interviews with 24 parents, spread across VIG Practitioners participating in the programme, upon completion of the 3-month intervention. Parents will receive all VIG sessions in person, and the Shared Reviews will be either in person or online. This will allow for maximum parental participation in the evaluation. Interviews will last approximately 60 minutes and as a thank you for their time, parents will be offered £30, in the form of a voucher (e.g., Amazon, Paypal, Love2Shop). This will not have an impact on state benefits that parents might be receiving. To reduce barriers to participation, we will be flexible with parent fieldwork. For example, interviews may be split over two, shorter sessions. We will not request permission to access the VIG session recordings because we will not include this in the evaluation analysis.

It is unlikely we will hit saturation because the Social Workers and families are expected to be different, with different experiences, especially since the 21 practitioners come from 4 different LAs with different CSC structures and practice standards. However, we will have ongoing discussions about what we are learning and if we feel we are starting to hear the same things with nothing new emerging then we would raise this with WWCS and discuss whether to end interviews, and how best to reallocate that evaluation budget elsewhere in the evaluation.

Method	Sample size	Time point
In-depth interviews with delivery leads	4-5 respondents	Early August 2021
Focus group with trainers and supervisors	4-8 trainers and supervisors	Early August 2021
Focus groups with VIG Practitioners in each area	Total of six groups (4-6 respondents in each group)	Early August 2021
Interviews with delivery leads and all participating VIG Practitioners in local areas	20-25	November/December 2021
A focus group with supervisors over video call	4-6 respondents	November/December 2021
Observations of four group supervision sessions	5-15 participants	August – December 2021
In-depth interviews with families	24 families	May/June 2021

Analysis

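### The February 2022 practitioner work-engagement score labelled post-intervention falls mid-delivery, and the sections disagree on when practitioners are assessed

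*Protocol*

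**What the plan says.** Protocol, Exploratory Analysis: the UWES-9 is administered, at interview or by email, "before delivery commences (in early July 2021) and again in February 2022". The use made of it is that "VIG Practitioner overall mean and dimension mean scores will be compared pre- and post-intervention", together with a comparison against a reference norm group. The section calls the analysis exploratory because there is no counterfactual group and only 21 practitioners. It says nothing about where the two dates fall in the programme.

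Protocol, Summary: intake runs to the end of March 2022, and "the intervention for all families will end by June 2022".

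Protocol, Interventions: the account of practitioner preparation states that "social and family workers have been supported to complete the VIG intervention with at least one 'pilot' family, under close supervision". The Participants section also describes practitioner training in the past tense, following the finalising of local authority partnerships by mid-March 2021. Neither section dates the training.

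Protocol, IPE Design Table: for set-up and for training, the method is "In-depth interviews with delivery leads, trainers and VIG Practitioners at the end of setup/implementation and at the end of delivery". The row on what difference VIG makes to practitioners, which includes engagement with their work, is also placed at the end of delivery.

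Protocol, Qualitative data collection - stage 2: at the area visits, "VIG Practitioners will be asked a few more quantitative questions about impact e.g., self-reported 'work engagement' etc". The methods table that follows dates "Interviews with delivery leads and all participating VIG Practitioners in local areas" to November/December 2021.

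**The concern.** A score described as post-intervention should be taken when the intervention is over, or the text should say that it is not. Here the second UWES-9 is taken while families are still being recruited and many courses are unfinished. A reader of the report would take a flat or falling score as no change over the whole programme, although the last months of delivery were not measured and some of any training gain may already be in the first score. Work engagement is a logic-model outcome for practitioners and a named interest of the process evaluation, so the label will be carried into the findings.

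The interview timings raise the same problem. Questions that the design table places at the end of delivery would be put to practitioners in November or December 2021, when few families could have completed a course. The stage 2 text adds work-engagement questions to those visits and does not say whether they are the UWES-9, or how they relate to the February score.

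**Working it through.** **Position of the February score.** Inputs: 1 to 28 February 2022 (Exploratory Analysis); intake to 31 March 2022 and delivery to June 2022, taken as 30 June (Summary).
- To close of intake: 1.9 months from 1 February, 1.0 month from 28 February.
- To end of delivery: 4.9 months and 4.0 months.

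**Courses that cannot be finished, on the protocol's forecast.** Inputs: 252 dyads allocated 1:1, so 126 to intervention; some 150 dyads randomised July to November 2021 (Secondary Analysis); courses of 3 to 4 months (Interventions).
- Randomised after November: 252 − 150 = 102, and 102/252 = 40%.
- Intervention arm: 102/2 = 51 of 126. A three-month course begun on 1 December ends on 1 March, so none of these is finished by 28 February.
- At most 126 − 51 = 75 of 126 (60%) can be finished.

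**Check under even intake (assumption).** Referral is uniform from 15 July 2021 to 31 March 2022 (259 days), with two weeks from referral to start. Starts therefore begin on 29 July, and 28 February is day 214.
- Three-month courses: finished if started by 28 November (day 122), 122/259 = 47%, or 59 of 126. In progress: (214 − 122)/259 = 36%, on average half done. Delivery completed: (122 + 92/2)/259 = 65%.
- Four-month courses: finished if started by 28 October (day 91), 91/259 = 35%, or 44 of 126. In progress: (214 − 91)/259 = 47%. Delivery completed: (91 + 123/2)/259 = 59%.
- At 1 February (day 187) the same sums give (95 + 92/2)/259 = 54% and (64 + 123/2)/259 = 48% of delivery completed.

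Even intake is slower than the protocol's forecast. With 75 intervention starts spread evenly over the 124 days from 29 July to 30 November, courses finished by 28 February are 75 × 91/124 = 55 to 75 × 122/124 = 74 of 126, or 44% to 59%.

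**November/December interviews, even intake.** Finished by 30 November: 126 × 2/259 = 1 (four-month courses) to 126 × 33/259 = 16 (three-month). Finished by 31 December: 126 × 33/259 = 16 to 126 × 63/259 = 31.

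**Position of the July score.** Mid-March to early July 2021 is 3.7 months, long enough for initial training and one pilot course. The wording ("social and family workers have been supported to complete the VIG intervention with at least one 'pilot' family") puts the pilot in the past. The process evaluation's first phase, set for early August 2021, is to follow completed training. This points to a July score taken after initial training, but it is an inference from tense and sequence. Fortnightly supervision, the Midpoint Review Day and the Accreditation Day are also part of training, and supervision sessions are still being observed from August to December 2021.

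**The case against.** The strongest reply is that the section already concedes what matters: with no comparison group and 21 people, no dates would let the comparison isolate an effect of the programme. That stands. A reader might infer that the timing is what prevents an effect being shown, or that a June 2022 score would cure it; the documents support neither. The concession does not mention timing, however, so the label remains inaccurate.

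Second, the text does say that the first score precedes delivery, and elsewhere the protocol uses the word intervention for the sessions with families. On that reading July is a fair starting point. This also stands, and it confines the criticism of the July score to an undisclosed, probable overlap with initial training. A reader might infer that the whole training gain is already in that score; with no training dates and some training still to come, that goes too far.

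Third, the November/December questions and a February email could coexist, since the stage 2 text does not name the UWES-9. That is possible, so this is an unclear relation and not a proven contradiction. The interview dates are different: the end of delivery and November/December 2021 cannot both hold. The Design section itself starts the second phase once the first parents have completed the baseline survey, which fits the earlier date and not the table. Parent interviews are to follow completion of the intervention, so families' own accounts are not affected.

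Finally, a reader might infer from the share of unfinished courses that more than half of delivery lies after every planned later measurement. That ignores courses in progress. By the end of February about 59% to 65% of delivery is done even under the slower, even intake.

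**Conclusion.** The point holds in a limited form. On the protocol's own dates the February 2022 score is a mid-delivery value, 4 to 5 months before delivery ends and with intake still open. About 40% of intervention dyads cannot have finished by then; this rests on the forecast of 150 dyads by November 2021 and a course of at least three months. The shares of courses finished (35% to 47%) and delivery completed (59% to 65%) at 28 February rest on assumed even intake and a two-week lag, and the protocol's faster forecast would raise them. That the July score follows initial training is probable but not stated. The end-of-delivery interviews in the IPE Design Table conflict with the November/December 2021 dates in the methods table.

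The consequence is minor: it concerns an exploratory measure in 21 practitioners and the process strand, and no primary or secondary outcome is affected. What the two scores can show is uncontrolled change over the first seven to eight months (6.9 to 7.8 months from early July to February).

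**What to change.** 1. Collect the final UWES-9 by email from all 21 practitioners at the end of delivery (June 2022) and keep February as a mid-delivery value. If that is not wanted, relabel February as mid-delivery.
2. Describe the July 2021 score as taken before trial delivery and after initial training, once the training dates are confirmed, and limit the conclusion to uncontrolled change during delivery.
3. Reconcile Exploratory Analysis, the IPE Design Table, and the stage 2 text and methods table. State whether the work-engagement questions at the November/December visits are the UWES-9, and either call those interviews mid-delivery or add an end-of-delivery contact.

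The cost is one nine-item email, a mode the protocol already allows, and some wording. It fits before the report due by the end of August 2022. The drawback is that some practitioners may have left by June 2022, so the number responding at each time should be reported.

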The primary analysis will be conducted according to the principle of intention to treat (AITT), recognising the possibility that some dyads allocated to the intervention will remain unexposed to the intervention. There is also a possibility that some dyads allocated to control, through error or subversion, are exposed to VIG. Essentially the trial data are analysed consistent with the allocation dyads received at randomisation regardless of whether they then went on to be exposed to VIG. This situation is slightly complicated by the challenges of missing data both at baseline and/or follow-up. These features of the data effectively create the following distinctions in the trial data:

- **The referred sample as randomised** – this sample contains complete records from the referral forms for all dyads referred and randomised.
- **The baseline sample as randomised** – this sample is all those dyads referred and randomised and who supplied the required data at baseline.
- **The follow-up sample at analysis** – this sample is all those dyads referred and randomised and who supplied complete data at follow-up. *Note*, we assume for child protection outcomes, obtained from administrative case files, there are no missing data at follow-up.
- **The completed cases sample at analysis** – this sample is all those dyads referred, randomised and who supply the necessary responses to the baseline and follow-up, such that the primary analysis described below can be conducted; that is prior to imputation
- **The imputed sample at analysis** – imputation at analysis will take different forms depending on which of the co-primary outcomes is considered (a full discussion of missing data and imputation strategy is provided below). For the primary outcomes derived from the MORS-SF scale the imputed sample at analysis contains all dyads referred and randomised, with either their observed values derived from the relevant items in the baseline and follow-up questionnaires, or where missing, their values on the relevant items required for the primary analysis filled-in using multiple imputation, should this prove a possible/viable strategy.

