Secondary analysis will consist of two sets of distinct analysis: first the derivation of sample estimates of the average effect of intention to treat on (1) parental self-efficacy (Karitane Parenting Confidence Scale); (2) Parental stress (Parental Stress Scale); and (3) the step-up/CSC escalation binary indicator. Second, for the primary analyses discussed above, for both co-primary outcomes, sample estimates of complier average causal effects (CACEs) will be obtained if it has proved possible to collect accurate take-up measures for individual dyads

Sample estimates of AITT for self-efficacy and parents stress will be obtained from fitting regression models to the relevant data consistent with the Equation [1] above, and using the same statistical procedures, where the dependent variables 'Y' and covariate 'X' are derived from the relevant scales and questionnaire data at baseline and follow-up. All model estimates will be derived from the completed cases sample files for the relevant data items.

A sample estimate of AITT for the step-up binary outcome will also be obtained as part of the secondary analysis. Sample estimates will be obtained from a linear probability model containing the following covariates, where the binary response is the dependent variable:

- Focal parent's age at randomisation (from the referral form)
- Focal baby's age in months at randomisation (from the referral form)
- Whether the father is present in the family home at randomisation (from the referral form)

The analysis will be performed on sample cases for those dyads randomised between July and November 2021. We anticipate that this sample will comprise some 150 cases. This analysis should not be affected by missingness. For binary outcomes, effect sizes will be reported as differences in adjusted incident rates.

If possible we will seek to obtain records on programme exposure for each dyad, whether allocated to intervention or control. If such indicators are of sufficient reliability and quality we propose to obtain complier average causal effects on the co-primary outcomes (Glennester & Takavarasha, 2013).

Exploratory Analysis

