It is possible that some parents will be aged under 16. Parents/infants likely to be eligible for the study may face multiple areas of disadvantage and challenge. Information will therefore be presented in a range of formats to ensure that it is easy to access and understandable by all. Throughout the recruitment process, LAs will make sure that young persons and participants from vulnerable groups will have sufficient understanding of the proposed project. Information will be presented in a way comprehensible to potential participants in the form of short accessible information sheets that Local Authorities can use to ensure that potential participants are fully informed.

After randomisation, participants who are allocated to receive treatment will be further informed about VIG: there is a client information sheet used by Babies1st that the practitioner talks through with a parent before starting VIG. Moreover, a bespoke animation for Babies1st will be used to introduce VIG to parents of babies.

All parents will also be issued with a withdrawal form and can withdraw from the study at any time by sending this to IFF. By doing so their data will be removed from the trial database and will not be further processed.

Information will be presented in a way comprehensible to potential participants. WWCS will create animations and short accessible information sheets that Local Authorities can use to ensure that potential participants are fully informed.

Parents may feel that their treatment by social services is conditional on their participation in the trial. All communications will overtly state that there is no obligation to take part, and that their decision will not affect their ongoing and future care.

Qualitative data collection - stage 1

The first phase of fieldwork, focusing on setup and implementation fieldwork will include:

- **4-5 in-depth interviews with delivery leads** from each of the participating areas, and Babies1st overall lead. These interviews will focus on experiences of elements such as recruitment of VIG Practitioners and parent dyads, training of VIG Practitioners, as well as any perceived risks to the programme and associated mitigation strategies. We expect these to last around 60 minutes.
- **Focus group with 4-8 trainers and supervisors** from Babies1st, to gain a deeper understanding of the training and guidance VIG Practitioners are provided with and what their support needs are seen to be.

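### Withdrawing from the study erases a randomised dyad's data, which conflicts with samples, bounds and a step-up analysis described as covering all dyads or free of missing data

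*Protocol*

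**What the plan says.** **The rule.** Under Consent procedures (Implementation and Process Evaluation), every parent is given a withdrawal form and "can withdraw from the study at any time by sending this to IFF". The consequence follows at once: "By doing so their data will be removed from the trial database and will not be further processed". The text sets no time limit, so the rule also applies after randomisation. It makes no exception for referral data, questionnaires already returned or local authority (LA) records.

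**What the analysis sections promise.**
- Analysis Plan, on the principle: "the trial data are analysed consistent with the allocation dyads received at randomisation regardless of whether they then went on to be exposed".
- Analysis Plan, on the referred sample: "this sample contains complete records from the referral forms for all dyads referred and randomised".
- Analysis Plan, on multiple imputation for the two MORS-SF outcomes: "the imputed sample at analysis contains all dyads referred and randomised".
- Analysis Plan, on child-protection outcomes: no missing follow-up data, stated openly as an assumption.
- Missing data and imputation: the extreme bounds are presented as free of any assumption about how data came to be missing.
- Secondary Analysis, on the step-up outcome in about 150 dyads: "This analysis should not be affected by missingness".

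None of these places mentions erased dyads. The sample-size section and Table 3 allow only for questionnaire non-response.

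**The concern.** An erased dyad has no row in the data set. It cannot be imputed, given an extreme value in the bounds, or scored for step-up, so the protocol's statements cannot all hold once one randomised family withdraws.

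Two safeguards are weakened. The step-up outcome comes from administrative records, so it would normally survive a parent's refusal of questionnaires; erasure removes that advantage. The bounds are meant to show the worst that missing data could do, yet they narrow as families are erased, although nothing more has been learned.

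A later analysis plan cannot repair this, because it cannot restore deleted records.

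**Working it through.** **1. Which analyses are touched**

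| Analysis | Stated coverage | Effect of an erased dyad |
|---|---|---|
| Complete-case primary | dyads with both questionnaires (141 of 252 expected) | extra loss only if both had been returned; 252 - 141 = 111 are expected to be absent anyway |
| Multiple imputation | all randomised | row absent, cannot be imputed |
| Extreme bounds | no missing-data assumption | row absent, receives no extreme value |
| Step-up | no missing data | row absent, outcome lost |

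**2. Precision, starting from the protocol's own figure**

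Inputs from the sample-size section: two-sided alpha 0.05, power 0.80, R² 0.50, 1:1 allocation, four sites. Table 3 gives completers by site of 67, 47, 13 and 13.

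- Harmonic mean = 4 / (1/67 + 1/47 + 1/13 + 1/13) = 21.05, so effective N = 4 × 21.05 = 84.2.
- MDES = (t0.975 + t0.80) × sqrt[(1 - R²) / (0.25 × N)] with N - 6 degrees of freedom = 0.437. This reproduces the stated 0.44.
- No withdrawal rate is given. If 2%, 5% or 10% of completers were erased, the MDES becomes 0.442, 0.449 or 0.462.
- The step-up sample of 150 would fall to 147, 142.5 or 135 at the same rates.

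The loss of precision is small. The issue is possible bias, and bounds that look too tight.

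**3. Step-up (illustrative)**

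Assumptions: 150 dyads split 75 and 75; true risk 20% in both arms (15 children each); 6 intervention dyads erased and no control dyads. The spurious difference is (15 - k)/69 - 15/75, where k is the number of erased children who had stepped up.

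| k | Calculation | Difference |
|---|---|---|
| 0 | 15/69 - 0.20 | +1.7 points |
| 1.2 (the average rate) | 13.8/69 - 0.20 | 0 |
| 3 | 12/69 - 0.20 | -2.6 points |
| 6 | 9/69 - 0.20 | -7.0 points |

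If the 6 erased dyads were controls, every sign reverses. With losses in both arms, say 10% of intervention and 2% of control (7.5 and 1.5 dyads), the range is:
- all erased children stepped up: 7.5/67.5 - 13.5/73.5 = -7.3 points;
- none did: 15/67.5 - 15/73.5 = +1.8 points.

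For scale, the standard error of the difference at 75 per arm and 20% risk is sqrt(2 × 0.2 × 0.8 / 75) = 6.5 points.

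**4. Width of the bounds (illustrative)**

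Table 3 implies 252 - 141 - 25 = 86 dyads without follow-up, a share of 86/252 = 34.1%. (Its response-pattern rows sum to 251 through rounding.) Assume equal missingness by arm, no covariate adjustment, and the full 0-35 scale. That range is a ceiling, because the protocol uses observed extremes.

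- Width with every dyad present: 35 × 2 × 0.341 = 23.9 points.
- If a share w of the 252 is erased, all from non-responders, the width is 70 × (86 - 252w) / (252 - 252w).
- w = 2%: 22.9. w = 5%: 21.5. w = 10%: 70 × 60.8/226.8 = 18.8.

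The true uncertainty is still 23.9. Restoring the erased dyads as rows that hold only arm and site gives (60.8 + 25.2)/252 = 34.1% again, and so the correct width.

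**The case against.** The best defence is that this is a deliberate protection. The parents are vulnerable, some may be under 16, they may fear that their care depends on taking part, and ethical approval has been given. The Analysis Plan labels complete child-protection data as an assumption, and Secondary Analysis says only that missingness should not matter. The primary analysis is barely touched. All of this stands. It bears on how the rule is changed and how serious the point is; it does not reconcile the sections.

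A reader might also infer four stronger claims that the protocol does not support.

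- **That stopping VIG means erasure.** The form is for leaving the study and goes to the evaluator. Nothing says that it is how a parent stops VIG. The Analysis Plan keeps dyads by allocation "regardless of whether they then went on to be exposed to VIG", and Secondary Analysis plans complier effects from exposure records. The protocol does not spell out the distinction, however.
- **That the intervention arm will lose more families, to VIG's advantage.** After randomisation, "participants who are allocated to receive treatment will be further informed about VIG", so contact does differ by arm, but no withdrawal rates are given. The section on missing data expects follow-up response to differ by arm and suggests that intervention families may respond more. That does not point to excess intervention withdrawals.
- **That the loss would be invisible.** The Randomisation section saves an allocation list for each site. Comparing used allocations with remaining rows may recover counts by arm. What is lacking is a commitment to do so.
- **That families in difficulty are the likeliest to withdraw.** This is plausible, but no passage says it.

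I have not seen the pages between the start of Data Protection and the staff biographies. Text there could limit the rule; nothing in the visible text does.

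**Conclusion.** The conflict is real and stands on the protocol's own wording: erasure on withdrawal cannot coexist with samples of all randomised dyads, complete child-protection data and assumption-free bounds. It falls mainly on the step-up outcome, the imputed analysis and the bounds.

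Its size cannot be fixed, because no withdrawal rate is given. In the illustrations, six erasures in one arm move the step-up difference by anything from +1.7 to -7.0 points, the latter only if all six had escalated and about one standard error in size. Erasing 10% of dyads, all non-responders, would make the bounds look up to about 5 points narrower than they should be. The direction of bias is unknown, and it is zero if erased children escalate at the average rate. The documents therefore do not support saying that the rule favours VIG or undermines the primary result. The point is worth acting on because the change is cheap and deletion cannot be undone.

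**What to change.** 1. **Form and Consent procedures, for parents not yet consented.** Separate three choices: stop questionnaires; stop further LA data linkage; erase data already held. State that stopping VIG alone is not withdrawal from the study.
2. **Data already collected.** Keep them in pseudonymised form and analyse them by allocation, unless the parent expressly asks for erasure.
3. **Erased dyads.** Keep and report an anonymous count by arm and site. In the bounds, add one row per erased dyad holding only arm and site, with the mean-imputed baseline, the missing-baseline indicator and the extreme outcome already specified.
4. **Wording.** Qualify the all-randomised and no-missing-data statements in the Analysis Plan, the no-assumption claim for the bounds in Missing data and imputation, and the missingness statement in Secondary Analysis.

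**Cost.** A revised form and consent wording, needing ethics and data-protection approval; no new data collection. Dyads already consented keep the old terms, so items 3 and 4 are needed for them in any case. In the two sites of 24 dyads the counts will be small, so their publication needs care over disclosure.
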